## **Technological background**

In the proposed studies it is important to compare the new technology, Fecobionics, to current state-of-the-art reference technologies. We expect Fecobionics to provide data that cannot be obtained with current technology and to reduce variation in measured variables.

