### **Reference testing techniques**

**Anorectal Manometry (ARM) with balloon expulsion testing (BET)** will be conducted with a standard single-use 8ch anorectal catheter (G-90150, MMS, Enschede, Netherlands). The catheter will be inserted with the subjects lying inside position with bent hip and knees. The bag will be placed in the rectum and pressure will be measured at 0.5cm distance in the anal canal. The following parameters will be evaluated: resting anal pressure, maximum anal squeeze pressure, the recto-anal inhibitory reflex (RAIR), urge volume, maximum tolerable volume, and expulsion time for the 50ml balloon.

**Defecography (fluoroscopy or MRI)** will be used as a reference for Fecobionics. A water-soluble paste will be injected into the rectum and serial x-rays will be taken during defecation. Defecography will be used to study several anorectal characteristics. The height of the colorectal anastomosis, any abnormality at the anastomosis such as narrowing, orientation of neo-rectum will be assessed in addition to usual measurements of the anorectal angle and the position of the pelvic floor at rest or during Valsalva (perineal descent). The presence of rectocele, rectal intussusception, and the ability to expel rectal contents will be evaluated. Balloon proctography can simplify the procedure of examining the ability to evacuate by providing a quick and clean test with minimal radiation.

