## Approach

**Device Characteristics and human recordings.** The integrated Fecobionics device is uniquely designed to improve diagnostics of anorectal disorders. The design integrates ARM, BET, defecography and FLIP. The new design features of the integrated device are shown in Figure 1 and include the inner bendable core that contains the sensors and a bag for distension made of 25 micrometer polyurethane. The core is easily bendable and contains electronic components such as pressure transducers, gyroscopes, and impedance electrodes as well as circuit boards for the central processing unit (CPU). A tube is used for filling of the bag after the placement in rectum to the urge-to-defecate level. All materials in the device are medical grade. The core and the bag provide a double layer protection for the electronic components. Our institutional review board did not have any concerns about the risks and safety of the device.

**Figure 1** shows the design of the Fecobionics device with the computer that also serves as a visual analog scale (VAS) for sensory evaluation in addition to displaying data. The core is made from medical grade resins and contains three pressure sensors placed at the front, rear and inside the bag. It also contains two gyroscopes used for determination of orientation and bending (the anorectal angle). Furthermore, eight pairs of electrodes that utilizes the FLIP principle to determine the geometry of the bag surround the core. The core also contains the CPU, multiplexer, amplifiers, and batteries. A valve and bag filling tube system as well as a safety thread are attached in the front of the device (not shown).

**Figure 2** shows schematics of novel analysis of the pressure signals from preliminary studies in healthy human subjects and patients with anorectal disorders. The left panel shows the front and rear pressure and the difference between them as function of time. Studies have demonstrated that defecation can be subdivided into five distinct phases. The difference in the two axial pressures (pointing forward and

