**Data analysis including statistics and sample size determination.**

A number of biomechanical parameters will be computed from the recorded data. These parameters include but are not limited to:

- Pressure difference between the rear and front ends (a measure of anal sphincter relaxation and key to the determination of phases of the defecatory process)
- Orientation and bending of Fecobionics for assessment of the anorectal angle

- Velocity of expulsion (as measured from the time difference between sensor data)
- Tension
- Strain (deformation) and displacement

Definitions of tension, strain and displacements can be found in the two books by the [name]. Sensory measures and clinical data will be related statistically to the mechanical measures. Endpoint data will be expressed as mean±SD if they can be considered normally distributed. Significance of the differences between two methods will be evaluated by ANOVA where appropriate and by multiple and single regression analysis. The results will be considered statistically significant when p<0.05 (2-tailed). Multiple regressions will be used to evaluate risk factors using causal and predictive analysis. Repeatability and distribution will be determined based on coefficient of variation (SD/mean) and used to evaluate accuracy.

The projected number of subjects, n, required to test a null hypothesis is given by the following equation:

$$n > \left[ \frac{[Z_{2\alpha} + Z_{2\beta}] \sigma}{\delta} \right]^2$$

where  $\alpha$  is the required probability of a Type I error,  $\beta$  is the required probability

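### SD/mean is set for every measured variable, but for absolute angles and the rear-front pressure difference it depends on the angle convention or becomes unstable near zero

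*Combined protocol and SAP*

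**What the plan says.** The section on data analysis, statistics and sample size lists the biomechanical parameters to be computed. The first two are "Pressure difference between the rear and front ends" and "Orientation and bending of Fecobionics for assessment of the anorectal angle"; expulsion velocity, tension, and strain and displacement follow. One sentence then covers variation: "Repeatability and distribution will be determined based on coefficient of variation (SD/mean) and used to evaluate accuracy". It is not limited to any type of variable. The same paragraph plans mean±SD for endpoints that can be considered normally distributed.

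Four other places bear on this:

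- Technological background expects the device to "reduce variation in measured variables" relative to reference technologies.
- Specific Aim 1 makes a description of the variation of the measured variables part of its milestone.
- Reference testing techniques makes defecography a reference for Fecobionics and has it supply "usual measurements of the anorectal angle and the position of the pelvic floor at rest or during Valsalva".
- Approach equates the bending recorded by the device's gyroscopes with the anorectal angle.

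No section says whether a straight device reads 0 or 180 degrees, which convention defecography uses, or which sign the pressure difference carries.

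**The concern.** A coefficient of variation has a clear meaning only for a positive quantity with a true zero. There, changing the unit changes the SD and the mean by the same factor, and the ratio stays put. An absolute angle has a conventional zero: shift or reflect it and the mean changes while the SD does not. A signed difference can have a mean near zero, where dividing by it makes the ratio very large, unstable or negative.

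Both variables matter to this study. The plan treats the pressure difference as key to dividing defecation into phases, and it presents the anorectal angle as an objective output of the device. If their variation is reported as SD/mean, a reader may take a feature of the scale for a property of the device. A comparison of angle variation with defecography would be open to the same error if the two methods were recorded on different conventions.

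**Working it through.** The documents give no CV, mean or SD for an angle or a pressure difference, so there is no planned figure to reproduce. All means and SDs below are assumptions chosen to show the behaviour.

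**1. Absolute angle.** Let the angle have mean theta and standard deviation SD. Recorded as 180 - theta, the SD is unchanged. The two CVs are SD/theta and SD/(180 - theta), and the second divided by the first is theta/(180 - theta), whatever the SD. With SD = 15 degrees:

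| theta | 180 - theta | SD/theta | SD/(180 - theta) | ratio |
|---|---|---|---|---|
| 90 | 90 | 16.7% | 16.7% | 1.0 |
| 100 | 80 | 15.0% | 18.8% | 1.25 |
| 120 | 60 | 12.5% | 25.0% | 2.0 |
| 130 | 50 | 11.5% | 30.0% | 2.6 |
| 140 | 40 | 10.7% | 37.5% | 3.5 |

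The ratio passes 3 only when theta exceeds 135 degrees, since 135/45 = 3.

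**2. Effect on a comparison, if conventions differed.** Suppose one method reads a bend of 40 degrees with SD 10, and the other an angle of 140 degrees with SD 15. The CVs are 10/40 = 25.0% and 15/140 = 10.7%, so the method with the smaller SD looks worse. On one convention the first becomes 10/140 = 7.1%, and the order agrees with the SDs.

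**3. Signed pressure difference.** With SD = 20 units:

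- mean 60: 20/60 = 33%
- mean 40: 20/40 = 50%
- mean 10: 20/10 = 200%
- mean 5: 20/5 = 400%
- mean -5: 20/(-5) = -400%

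These are different data sets with the same spread, not one data set rescaled. Reversing the sign convention on one data set changes only the sign of the CV.

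Sampling error adds to this. In 100,000 simulated normal samples of n = 30 with SD 20, the central 95% range of the sample CV (as a ratio) was:

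- mean 60: 0.24 to 0.43
- mean 20: 0.65 to 1.63
- mean 10: 1.06 to 6.6
- mean 5: -29 to 37, with 8% of samples negative

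At a mean about three SDs from zero the CV is stable; near zero it is not usable.

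**4. Where SD/mean works.** A simulated expulsion time gave a CV of 51.0% both in its original unit and after multiplying by 60. The same holds for velocity and volume. For the maximum angle difference, listed among the Aim 1 endpoints, the arbitrary zero cancels: (180 - a) - (180 - b) = b - a, so the CV is the same in absolute value under either convention. It would fail there only if the mean change were near zero.

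**5. Which SD.** I find no schedule of repeat Fecobionics tests in the documents. With one value per patient, SD/mean across patients describes between-patient spread, which is not repeatability. With an assumed between-patient SD of 20, within-patient SD of 5 and mean of 120 degrees, the total CV is sqrt(20² + 5²)/120 = 17.2%, while the within-patient CV is 5/120 = 4.2%.

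**The case against.** The strongest reply is that this is one general sentence in a study described as exploratory, with regression as its main tool. No primary inference and no sample-size calculation uses the CV. The sentence does not name angles or pressure differences, and the CV suits several of the listed outputs. Mean±SD is planned as well, which is much of what is being asked for. All of this is fair and limits the weight of the point. It does not remove it: mean±SD depends on a judgement of normality and is not the statistic assigned to repeatability, and an SD comparison of angles still needs a stated convention.

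A reader might also infer more than the documents support:

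- *That the choice of zero decides which method wins on the angle.* No section ranks methods by CV. Differences between methods go to ANOVA and regression. The expectation of reduced variation is background, and the Aim 1 milestone is descriptive.
- *That the device and defecography use supplementary angles.* No section says so. The text presents the device's bending as the same anorectal angle; the gap is that the convention is unstated.
- *That the pressure difference crosses zero.* This is plausible for a signed difference followed over time, but the text does not show it and the figure is not available. The summary value to be analysed is also not defined, and a peak well away from zero would have a stable CV.
- *That CVs will generally be several times too large or too small.* The angle ratio is 1.0 at 90 degrees, and the documents give no angle values.
- *That the reduced-variation claim cannot be judged at all.* Expulsion time, shared by the balloon test and Fecobionics, has a valid CV, and SDs will be reported for normally distributed endpoints.

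**Conclusion.** The point holds in a limited form. The plan applies SD/mean without restriction, and for two of its listed parameters that statistic either depends on an unstated angle convention or is unstable if the mean lies near zero. The angle effect is exactly theta/(180 - theta), ranging in the cases tabulated from none at 90 degrees to 3.5-fold at 140. The pressure effect depends on the ratio of mean to SD: small when the mean is about three SDs from zero, severe when it is a quarter of an SD. Which case applies here is unknown, because the documents give neither means nor SDs.

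Expulsion time, velocity and volume are not affected, nor is the maximum angle difference as far as the choice of zero goes. The primary analysis is not at risk. What is at risk is the reported variation of absolute angles and pressure differences, and any comparison of angle variation with defecography. Separately, the plan uses the CV to evaluate accuracy. A CV describes spread, not closeness to a reference value.

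**What to change.** Replace the sentence on the coefficient of variation with text to this effect:

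> SD/mean will be reported only for positive variables with a true zero (expulsion time, velocity, volume). For absolute angles and the rear-front pressure difference, the SD will be reported in native units with a 95% confidence interval. It will be labelled as between-patient, or as within-patient where repeat measurements exist. The angle convention (reading of a straight device), the sign of the pressure difference and the summary value taken from its time course are defined before analysis. Angle variation will be compared with defecography only after both methods are expressed on one convention. These measures describe variation and will not be described as accuracy.

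The cost is a few sentences in the SAP and a fixed angle conversion in the analysis code. It needs no additional patients, tests or data. The definitions should be settled before the data are analysed, so that the choice of zero or sign is not made with the results in view.

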### Specific Aim 1: Anorectal pathophysiology of LARS patients

Objective: use fecobionics to obtain physiological and pathophysiological signatures of anorectal function in a heterogeneous group of LARS patients. Based on the epidemiology and symptomatology of LARS, it is expected that the heterogeneous group will contain an almost equal number of LARS patients with incontinence, frequency and urgency, and those primarily with constipation and feelings of incomplete emptying. Due to the spread (heterogeneity) in the patient group regarding symptoms, regression analysis will be the primary statistical tool to associate symptoms with experimental findings. We will also compare to age- and sex-matched healthy controls from already conducted studies.

Milestone: Describe the mechanosensory signature, variation of the measured variables, and computed endpoints in LARS patients.

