of a Type II error,  $\delta$ , is the estimated difference between the means of two comparison groups, and  $\sigma$  is the estimated standard deviation of the means in each of the two comparison groups. We assume  $2\alpha < 0.05$  ( $Z_{2\alpha} = 1.96$ ) and  $2\beta < 0.10$  ( $Z_{2\beta} = 0.84$ ). We assume the values of mean difference, d, and standard deviation, s, from previous experience in the clinical laboratory and from reported data in the literature on the involved patient groups and the sensitivity and specificity of current tests. An alternative method is to use sample size estimation based on the Altman-Bland analysis (<http://wwwusers.york.ac.uk/~mb55/meas/sizemeth.htm>). Preliminary data on expulsion time using BET and Fecobionics were used in the sample size analysis. Data variation (SD, SE) was computed for preliminary data. The confidence interval for the 95% limits of agreement was computed and n was determined. For both analyses, given the exploratory nature of the study, we consider a heterogeneous group of patients and that 80% of operated patients will develop LARS. Using these boundaries and criteria, we arrived at a sample size of 30 in the Aim 1 study for evaluation of statistical significance, association and risks. Though the material may be too small to account for confounders, we will obtain clear indications of risks and causes. For the comparison with previously studied subjects, we have a pool of 35 healthy asymptomatic subjects, 20 patients with FI and 15 patients with constipation to compare with.

**Clinical Assessments of device safety:** Fecobionics have now been used in more than 70 human studies without any incidents or adverse effects. In addition, a safety study has been performed in 12 pigs without any device related issues or damage to anorectal mucosa (yet unpublished data). Since Fecobionics is still an experimental device, we will pay attention to safety. If any safety issue occurs, it will be characterized and reported. Additional data obtained will include procedural duration, sensation

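### The sample size text declares 2β below 0.10 but uses Z = 0.84, the value for β = 0.20, and neither sizing route described covers the primary regression

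*Combined protocol and SAP*

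**What the plan says.** All but one of these statements are in the section on data analysis, statistics and sample size determination.

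- The equation is introduced with "The projected number of subjects, n, required to test a null hypothesis is given by the following equation". It is n > [(Z_2α + Z_2β)σ/δ]², with no factor for two groups.
- The effect δ is framed as a contrast of two groups, not of two readings on one patient.
- The spread σ is described in these words: "is the estimated standard deviation of the means in each of the two comparison groups".
- 2α is set below 0.05 with Z = 1.96. The Type II entry reads "2\beta < 0.10$ ( $Z_{2\beta} = 0.84". β itself is defined as the probability of a Type II error.
- A second route, by Altman-Bland analysis, is offered as an alternative: "Preliminary data on expulsion time using BET and Fecobionics were used in the sample size analysis", and "The confidence interval for the 95% limits of agreement was computed and n was determined".
- The section then gives 30 patients for Aim 1 and says that this number serves significance testing, association and risk. It calls the study exploratory and concedes that the sample may not allow for confounders, but still promises clear pointers to risks and causes.

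The analysis is described differently. Under Specific Aim 1, "regression analysis will be the primary statistical tool to associate symptoms with experimental findings". The data analysis section adds: "Multiple regressions will be used to evaluate risk factors using causal and predictive analysis".

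**The concern.** The declared error rate and the deviate beside it cannot both be right. A reader who relies on the error rate takes the chance of a missed effect to be at most 10%, or 5% if the factor of 2 is taken literally. A reader who relies on the deviate takes it to be 20%.

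The definitions do not settle what was compared. The formula has the one-sample or paired form, while δ and σ are described for two groups.

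The stated purpose of the 30 patients also reaches beyond the calculation. Both routes concern a difference in means or agreement between methods, yet the main analysis is a regression of symptoms on measurements. A reader could take a null regression result as evidence of no association, believing that the sample had been sized to find one.

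**Working it through.** **Inputs from the documents.** Z = 1.96 for 2α = 0.05; Z = 0.84 for 2β < 0.10; the formula above; n = 30. δ, σ, the SD of the differences and the target width for the limits of agreement are not printed.

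**The plan's own figure.** Without δ and σ, 30 cannot be reproduced. Solving backwards, the formula gives exactly 30 only if δ/σ = (1.96 + 0.84)/√30 = 2.80/5.477 = 0.511.

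**Which error does 0.84 represent?** The upper-tail area of the standard normal beyond 0.84 is 0.2005, and the two-tail area is 0.401. So 0.84 means β = 0.20, or 2β = 0.40 in the plan's notation. The deviate for β = 0.10 is 1.282. The plan gets 1.96 from 2α = 0.05 by putting 0.025 in each tail; the same reading of 2β = 0.10 puts 0.05 in the tail and gives 1.645. No reading of 0.10 gives 0.84.

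**Effect on the formula, for any δ and σ.** Both cancel in the ratio:

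- As printed: (1.96 + 0.84)² = 7.84.
- β = 0.10: (1.96 + 1.282)² = 10.51; 10.51/7.84 = 1.34.
- 2β = 0.10: (1.96 + 1.645)² = 13.00; 13.00/7.84 = 1.66.

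**What 30 detects in a paired comparison**, with σ the SD of within-patient differences:

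| Power | Normal formula, δ/σ | By t-test |
|---|---|---|
| 80% | 2.80/√30 = 0.51 | 0.53 |
| 90% | 3.242/√30 = 0.59 | 0.61 |
| 95% | 3.605/√30 = 0.66 | 0.68 |

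**Does σ fit the formula?** A paired comparison needs the SD of within-patient differences. An independent-groups comparison needs the SD between patients in each group, and the printed n must be multiplied by (1 + n1/n2) to give n1, which doubles it per group when the groups are equal. A standard deviation of means is, taken literally, a standard error. The printed definition matches neither design.

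**What 30 gives for the regression** (one two-sided test at 0.05, approximately bivariate normal data, Fisher z with standard error 1/√27):

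- 80% power: tanh((1.96 + 0.842)/√27) = tanh(0.539) = 0.49.
- 90% power: tanh((1.96 + 1.282)/√27) = tanh(0.624) = 0.55.
- 95% CI for an observed r of 0.30: tanh(0.3095 ± 1.96/√27) = -0.07 to 0.60.
- With Bonferroni correction over an assumed 5 or 10 tests, the correlation detectable at 80% power rises to tanh((2.576 + 0.842)/√27) = 0.58 or tanh((2.807 + 0.842)/√27) = 0.61.

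**What 30 gives for limits of agreement.** The standard error of a limit is s√(1/30 + 1.96²/(2×29)) = 0.316s, where s is the SD of the differences. The 95% CI is then about ±1.96 × 0.316s = ±0.62s around each limit.

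**The case against.** The best defence is that the wrong pairing may never have affected the number. The only sentence saying that n was determined follows the limits-of-agreement interval, and that route has no β. This stands, and it limits the conclusion. A reader might infer that 30 should have been 41 (30 × 1.34 = 40.2) or 50 (30 × 1.66 = 49.7). That follows only if the formula itself gave exactly 30, which nothing in the documents shows. Nor does the plan state a power of 90% anywhere; it states an error rate.

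A second defence is that the formula is right for its purpose. Every patient has both Fecobionics and the conventional balloon expulsion test, the analysis section speaks of differences between two methods, and the sizing data are expulsion times from those two tests. For that comparison the paired form is correct. This largely stands: a reader might infer that the formula itself is wrong and n should be doubled, but the firm defect is the definition of σ. Nor is there evidence that a standard error was actually entered, since the same section elsewhere speaks simply of a standard deviation and lists SD and SE separately.

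Third, an exploratory study need not power its regression, and the plan admits a limit on confounders. That is fair. But the admission does not say how strong an association 30 patients can detect, and the text still presents 30 as reached for association and risk.

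A reader might also infer that the comparisons with the earlier healthy, incontinent and constipated subjects are underpowered. The plan makes no power claim for them, so they form no part of this point.

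**Conclusion.** The point holds as an error in the stated justification, and it should be fixed. The contradiction between the declared error and Z = 0.84 is certain under either reading of the notation. The factors 1.34 and 1.66 need no assumption about δ or σ, but they apply to the printed formula only. The documents do not establish that 30 is inadequate, and nothing here bears on conduct.

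The definition of σ needs correcting whichever comparison was meant. The claim that 30 serves association and risk is not supported by either route described. For the regression, the figures of 0.49 and 0.55 rest on a single test and approximate bivariate normality. The LARS score is a discrete sum, only patients with LARS are enrolled, and many parameters are planned, so these figures are a guide and probably a favourable one.

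**What to change.** Keep n = 30 and change the wording.

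(a) Make β and Z agree. If 0.84 was used, state β = 0.20 (80% power). Otherwise use 1.282 for β = 0.10 or 1.645 for 2β = 0.10. In each case give the δ/σ that 30 detects in a paired comparison: about 0.51, 0.59 or 0.66 at 80%, 90% or 95% power (0.53, 0.61 or 0.68 by t-test).

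(b) Name the comparison that was sized. If it is Fecobionics against balloon expulsion in the same patients, say so and define σ as the SD of within-patient differences. If independent groups were meant, add the factor (1 + n1/n2) and define σ as the between-patient SD. Either way, remove the words that make σ a standard deviation of means.

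(c) Stop presenting this calculation as sizing the regression. Add that, for one two-sided test at 0.05 and approximately bivariate normal data, 30 patients detect an absolute correlation of about 0.49 at 80% power (0.55 at 90%), with less power after any correction for multiple tests. Soften the promise about risks and causes to match.

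(d) Print the original inputs. If they cannot be recovered, say so and give the precision of 30: a 95% CI of about ±0.62 SD of the differences around each limit of agreement. Do not say that 30 was chosen on feasibility, because the documents give no basis for that.

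The cost is protocol text and a search for the original inputs, with no extra patients and no change to procedures. The downside is that the stated power looks less favourable and the main analysis is seen to detect only fairly strong associations.

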In a prospective study assessing consecutive patient's functional outcome post low anterior resection in our unit since January 2016, 34 patients have had their defunctioning stoma closed to date with 4 months follow up. 73.5% of our patients were experiencing major LARS. Approximately half of the patients had persistent symptoms at 2 years post stoma closure: 65.5% (19/29) and 46.2% (6/13) had major LARS at 12 and 24 months respectively. Hence, the figures from our unit correspond to reports from other centers Worldwide.

Unfortunately, there is no cure for LARS at present. Biofeedback treatment and nerve stimulation sacral nerve stimulation or tibial nerve stimulations with stimulators such as the Acutens seems to provide some symptomatic relief for some patients. The cause of LARS is thought to be multifactorial and difficult to define. Therefore, this trial is designed to use Fecobionics, a new Hong Kong based innovation, to provide new mechanistic insights regarding anorectal physiological function post low anterior resection. This will help us to understand the condition better and hopefully to improve their treatment options.

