### **New technology**

**Fecobionics** is a novel device, a simulated faeces, that we currently are testing in healthy subjects and in patients suffering from fecal incontinence and constipation (RGC funded proposal “Unraveling anorectal function and biomarker signatures in patients suffering from subtypes of defecatory disorders”). Fecobionics records pressures, orientation, bending, shape, and viscoelastic properties during defecation. It is made of a 10 cm long and 12 mm wide core of medical grade resin that contains multiple electronic sensors and circuit boards. A bag is mounted on the bendable core. Pressure transducers are placed at the front, rear and inside the bag, in addition to two gyroscopes for orientation and angle measurements. A novelty of Fecobionics is that it measures pressures in axial direction (in the direction of flow) in contrast to current technologies and that it integrates almost all current anorectal functional tests into a single test that only takes minutes to perform without the use of radiation or expensive equipment. Since the Fecobionics technology was developed by the PI [name], we are currently the only clinical research group with access to the technology. This gives us a unique opportunity to become the leaders in the field.

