
This proposal will result in a new paradigm in evaluation of LARS. The simulated faeces technology will potentially replace current tests as it provides an integration of measurements from multiple tests of anorectal diagnostics. Our expected outcome is to characterize abnormal pressures, forces and topographic changes in the neo-rectum and anal canal during defecation in LARS patients, to help with understanding of the cause of their symptoms to guide and improve LARS management.

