## **Research Design and Methods**

The overall goal of this proposal is outlined in the specific aims section. Specifically, we will target anorectal diagnostics of LARS patients to be conducted in the Department of Surgery at Prince of Wales Hospital in Hong Kong. In both studies listed below, we aim to recruit a heterogeneous group of patients to allow us to assess the effect of several underlying risk factors. In both studies, we will study the patients after closure of defunctioning stoma as we deem it impossible to carry out anorectal functional studies in patients with low rectal cancer before their rectal cancer surgery and assessing anorectal function post LAR before defunctioning stoma closure will produce unreliable, irrelevant data.

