#### **Inclusion Criteria:**

1. Patients 18 years of age or older with history of LARS over 3 months.

2. Informed, written consent by the patient

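### A difference between LARS patients and healthy subjects combines operation, cancer treatment and syndrome, so the plan should not attribute it to LARS

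*Combined protocol and SAP*

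**What the plan says.** The expected outcome, under Impact, is to "characterize abnormal pressures, forces and topographic changes in the neo-rectum and anal canal during defecation in LARS patients", in order to understand why these patients have symptoms and to improve their management. Under Specific Aim 1, "regression analysis will be the primary statistical tool to associate symptoms with experimental findings". The comparison with unoperated people is an addition: "We will also compare to age- and sex-matched healthy controls from already conducted studies". The data analysis section gives the pool: "we have a pool of 35 healthy asymptomatic subjects, 20 patients with FI and 15 patients with constipation to compare with".

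Three further passages fix who is compared with whom.

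- The first inclusion criterion is "Patients 18 years of age or older with history of LARS over 3 months".
- Research Design and Methods places testing after stoma closure and explains the lack of a baseline: "we deem it impossible to carry out anorectal functional studies in patients with low rectal cancer before their rectal cancer surgery".
- The section on the new technology says that the device is being tested "in healthy subjects and in patients suffering from fecal incontinence and constipation". It does not mention LAR. That these are the pooled comparators is an inference.

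The data analysis section calls the study exploratory and concedes that the sample may be too small to deal with confounders. It then says that risks and causes will nevertheless be clearly indicated.

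**The concern.** The healthy comparison is where a reader will look for what is abnormal in LARS. The people in it differ in more than the syndrome: one side has had a rectal resection with an anastomosis, in some cases with chemotherapy or radiotherapy, and the other side is not described as having had any of these. Matching on age and sex does not touch that difference.

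A finding against healthy subjects could be just as common in operated patients who function well. It would then explain none of the symptoms, yet could be reported as a mechanism of LARS. The plan's only caveat is about sample size, which is a different problem.

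**Working it through.** **The plan's own figure.** The sample size of 30 cannot be reproduced, because the mean difference and SD are not stated. Back-solving the plan's formula gives a standardised difference of (1.96 + 0.84)/√30 = 0.511. The point here does not depend on that figure.

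**Inputs from the documents.** There are 30 LARS patients, 35 healthy subjects, 20 with faecal incontinence and 15 with constipation. All LARS patients are post-LAR; no other group is described as such. The plan's multipliers are 1.96 and 0.84, which sum to 2.80 (two-sided 5%, about 80% power).

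**Step 1: what the healthy contrast estimates.** Let μ be the healthy mean of a measured variable, *a* the effect of operation and cancer treatment, and *s* the added effect of the syndrome.

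- Healthy: μ
- LARS patients: μ + *a* + *s*
- Difference: *a* + *s*

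The indicators for operation and syndrome are identical in these 65 people. The design matrix (intercept, operation, syndrome) has rank 2 with 3 columns. An observed difference of 0.70 SD fits *a* = 0.70 and *s* = 0 exactly as well as *a* = 0 and *s* = 0.70.

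**Step 2: the other two groups.** Giving incontinence and constipation their own effects adds two columns and two groups. The rank is then 4 out of 5, and *a* and *s* remain inseparable. Full rank (4 out of 4) is reached only by replacing the syndrome term with symptom effects assumed equal in operated and unoperated people. The documents do not state that assumption.

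**Step 3: more patients.** The detectable difference is 2.80 × √(1/n₁ + 1/n₂). For 30 against 35 it is 0.70 SD. With ten times as many in each group it would be 0.70/√10 = 0.22 SD, but the quantity estimated would still be *a* + *s*.

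**Step 4: what would separate the two.** Adding operated patients without LARS (mean μ + *a*) gives rank 3 out of 3. The plan assumes that 80% of operated patients develop LARS, so about 20% do not: 30/0.80 = 37.5 operated patients per 30 with LARS, or about 8 without.

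**Step 5: the price of doing this within 30 patients.** The splits are assumptions; the formula is that of Step 3.

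| Contrast | Groups | Detectable difference (SD) |
|---|---|---|
| LARS v healthy, as planned | 30 v 35 | 0.70 |
| LARS v healthy, 20 LARS patients | 20 v 35 | 0.78 |
| LARS v operated without LARS | 20 v 10 | 1.08 |
| LARS v operated without LARS | 22 v 8 | 1.16 |
| Two LARS symptom types, as planned | 15 v 15 | 1.02 |
| Two LARS symptom types, 20 LARS patients | 10 v 10 | 1.25 |

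The last two rows use the expectation under Specific Aim 1 that the two symptom types will be almost equally common.

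**The case against.** The strongest reply is that the healthy comparison is secondary. The primary regression compares operated patients with one another, so the operation is common to all of them and the aliasing does not arise. No passage rests the explanation of symptoms on the healthy contrast alone. This stands, and it limits the point to the secondary comparison and to what is concluded from it. The plan also labels itself exploratory, explains the missing baseline, and records tumour treatment and anastomotic level. None of that names the missing operated control, and an exploratory label excuses low power rather than attributing an effect to the wrong source.

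Three stronger readings are tempting, and the documents do not support them.

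- A reader might take the unit's follow-up figures, "65.5% (19/29) and 46.2% (6/13) had major LARS at 12 and 24 months respectively", as showing how many operated patients without LARS are being left out. The remainder are patients without *major* LARS. They include minor LARS (scores 21–29 on the questionnaire), which the criteria do not exclude.
- A reader might infer that LARS-only entry narrows the symptom range and costs the primary regression a known amount of power. Entry requires a history of LARS, not a current score, and recruitment aims at a broad scale of symptoms. Nor do the documents say that the total score is the symptom variable. No size can be put on this.
- A reader might conclude that the operation does account for any difference from healthy subjects. The documents give no measurements in operated patients who function well, so the size of *a* is unknown. The point is that it cannot be separated, not that it is large.

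**Conclusion.** The point holds for the secondary comparison. The LARS-versus-healthy contrast is a valid description of people who have had the operation and have the syndrome. It cannot be attributed to LARS or its symptoms, at any sample size and with any of the listed comparator groups, unless a further assumption is made. The conclusion rests on reading the comparators as unoperated. The documents do not say so outright, but they describe none as post-LAR, and prior LAR is implausible in healthy asymptomatic people.

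The primary regression is not aliased in this way and remains the place for statements about symptoms, subject to the plan's own caveat about confounders. The defect lies in what may be concluded, and wording can correct it. It does not by itself require a different study population.

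**What to change.** Make three changes.

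1. Under Specific Aim 1 and in the data analysis section, state that differences from healthy subjects describe the state 'after LAR with LARS' and are not attributable to LARS.
2. Under Impact and in the data analysis section, rest any statement about the cause of symptoms on the regression within the LARS patients.
3. List as a limitation that no operated patients without LARS are tested, and say that this is separate from the small sample.

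This needs no patients, tests or data beyond those planned. The downside is a narrower conclusion from the healthy comparison.

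The sponsor may also consider giving 8–10 of the 30 places to operated patients without LARS. That would separate syndrome from operation, but it leaves 20–22 LARS patients, thins the two symptom types to about 10 or 11 each, and detects only about 1.1 SD at 20:10. It would also put patients without the syndrome through an experimental device test and defecography. It is a trade-off to weigh, not a required change.
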